3.3.2 Follow-up for withdrawn subjects

Participants who report an inability to smoke research study cigarettes will be asked to complete a final MRI scan visit before being withdrawn from the study.

4.0 Recruitment Methods

4.1 Identification of subjects

All recruitment for this study will be routed through IRB Protocol #2213 which will also serve as the initial recruitment point of contact.

4.2 Recruitment process

Interested volunteers will complete a brief phone screen to determine preliminary eligibility and to learn more about the study. Interested and eligible participants will be scheduled for an in-person screening visit. Subjects that were unable to be contacted via phone will be sent an email asking them to reach out to the study team if they are interested.

4.3 Recruitment materials

The study will be described to interested volunteers over the phone using the phone screening script.

4.4 Eligibility/screening of subjects

Study staff will collect preliminary eligibility information over the phone. A full script and screening questions for this study are in the “Consent Forms and Recruitment Materials” section of the IRB application.

After a participant has met preliminary eligibility criteria over the phone, they will be scheduled to complete a final screening over the phone or ZOOM to determine study eligibility. See “7.0 Study Design and Procedures” and “Supporting Documents” for details on the screening assessment tools.

5.0 Consent Process and Documentation

5.1 Consent Process

5.1.1 Obtaining Informed Consent

5.1.1.1 Timing and Location of Consent

Screening portion: Subjects will have the screening portion of the study explained to them in detail over a phone call. They will have the opportunity to ask any questions and then will be asked to give their verbal consent to take part in the screening portion.

Randomization/MRI portion: During the phone screen, participants will have the study explained to them in detail, and be mailed a long form consent form to look over before their first MRI visit. They will have the opportunity to ask questions at both visits and then will be asked to sign their consent form at the MRI visit.

5.1.1.2 Coercion or Undue Influence during Consent

Once potential study volunteers are identified they will be given information about the study and offered the opportunity to participate. The researchers obtaining consent will be instructed to clearly indicate that the participant's enrolling in the trial is purely voluntary and the researchers will not offer comments about whether they believe the participant should enroll in the study or not. Given the number of contacts and visits involved in the study protocol, the compensation provided to the participant is modest.

5.1.2 Waiver or alteration of the informed consent requirement

N/A

5.2 Consent Documentation

5.2.1 Written Documentation of Consent

The consent process will be documented in writing as follows::

- The current IRB approved long form written consent form will be used.
- The subject will sign the consent form during their MRI visit after both screenings have taken place.
 - A copy of the consent form will be provided to the subject/representative. Whenever possible the consent form will be provided to the subject in advance of the consent discussion.

5.2.2 Waiver of Documentation of Consent (Implied consent, Verbal consent, etc.)

Volunteers who are interested in the study will be asked to provide verbal consent to allow the researcher to screen them for the study during a phone and a remote screening contact. First, volunteers will provide informed verbal consent prior to completing a brief phone screen to determine preliminary eligibility. Second, volunteers who meet preliminary eligibility, will complete a more in-depth screening assessment via ZOOM to determine final study eligibility. Volunteers will be emailed an electronic copy and mailed a paper copy of the Summary Explanation of Research prior to the final phone screen. Participants will be asked if their screening information can be retained so that the study team will know reasons that participants are not eligible for the study. The screening takes place prior to the randomization portion of the study and involves low risk procedures.

In addition, participants who are not eligible for the study, or those who begin the screening procedures but are not interested in completing it after learning more about the study, will be asked if they would be interested in being contacted for future studies being conducted by our research team. They will be informed that by providing their name and phone number, they will be consenting to allow the study team to contact them in the future.

5.3 Consent – Other Considerations

N/A

5.3.1 Non-English Speaking Subjects

5.3.2 Cognitively Impaired Adults

5.3.2.1 Capability of Providing Consent

5.3.2.2 Adults Unable To Consent

5.3.2.3 Assent of Adults Unable to Consent

5.3.3 Subjects who are not yet adults (infants, children, teenagers)

5.3.3.1 Parental Permission

5.3.3.2 Assent of subjects who are not yet adults

6.0 HIPAA Research Authorization and/or Waiver or Alteration of Authorization

6.1 Authorization and/or Waiver or Alteration of Authorization for the Uses and Disclosures of PHI

Check all that apply:

- Not applicable, no identifiable protected health information (PHI) is accessed, used or disclosed in this study. [Mark all parts of sections 6.2 and 6.3 as not applicable]
- Authorization will be obtained and documented as part of the consent process. [If this is the only box checked, mark sections 6.2 and 6.3 as not applicable]
- Partial waiver is requested for recruitment purposes only (Check this box if patients' medical records will be accessed to determine eligibility before consent/authorization has been obtained). [Complete all parts of sections 6.2 and 6.3]
- Full waiver is requested for entire research study (e.g., medical record review studies). [Complete all parts of sections 6.2 and 6.3]
- Alteration is requested to waive requirement for written documentation of authorization (verbal authorization will be obtained). [Complete all parts of sections 6.2 and 6.3]

6.2 Waiver or Alteration of Authorization for the Uses and Disclosures of PHI

6.2.1 Access, use or disclosure of PHI representing no more than a minimal risk to the privacy of the individual

6.2.1.1 Plan to protect PHI from improper use or disclosure

Information is included in the "Confidentiality, Privacy and Data Management" section of this protocol.

6.2.1.2 Plan to destroy identifiers or a justification for retaining identifiers

All identifiers stored electronically will be permanently deleted, including the keys linking participant ID numbers to their identifying information and paper consent forms will be shredded before disposal according to federal regulations and institutional policies.

6.2.2 Explanation for why the research could not practicably be conducted without access to and use of PHI

Information must be obtained from the subject during recruitment to determine/confirm eligibility. The screening visits will collect PHI to confirm eligibility (date of birth) and to allow for scheduling/reminders of future visits which requires us to have complete contact information.

6.2.3 Explanation for why the research could not practicably be conducted without the waiver or alteration of authorization

Determining/Confirming eligibility prior to obtaining consent will ensure only eligible subjects are enrolled in the study. Several factors make the collection of written informed consent prior to the randomization visit impractical, including; time constraints with the use of the MRI facility, the requirement that subjects record their daily cigarette usage between screening determination and the randomization visit, the need to prepare product for dispensation

between eligibility determination and the randomization visit, and the risk of unnecessary burden on volunteers.

6.3 Waiver or alteration of authorization statements of agreement

Protected health information obtained as part of this research will not be reused or disclosed to any other person or entity, except as required by law, for authorized oversight of the research study, or for other permitted uses and disclosures according to federal regulations.

The research team will collect only information essential to the study and in accord with the 'Minimum Necessary' standard (information reasonably necessary to accomplish the objectives of the research) per federal regulations.

Access to the information will be limited, to the greatest extent possible, within the research team. All disclosures or releases of identifiable information granted under this waiver will be accounted for and documented.

7.0 Study Design and Procedures

7.1 Study Design

This is a two-arm, randomized, double-blind parallel group trial. Smokers will be randomly assigned to smoke very low nicotine content (VLNC) (n=50) or normal nicotine content (NNC) (n=25) SPECTRUM cigarettes for 6 weeks. Participants and study staff will be blind to the experimental cigarette allocation until the study is complete. The groups will be stratified by gender.

7.2 Study Procedures

7.2.1 Final remote screen (Week 0)

A Penn State Health Zoom meeting link will be emailed to participant for the previously scheduled time.

A standardized smell test (this standardized test includes a No. 2 pencil and a pamphlet that the participant will complete on the Zoom meeting to allow the study team member to oversee the completion; the test will be scored over the Zoom session), paper cigarette logs, folder, written consent form, summary explanation of research, welcome letter and visit reminder card will be mailed to the participant to arrive before scheduled Zoom meeting. If there is a delay in the mail, the Zoom screening visit will be rescheduled.

The following information will be collected to determine eligibility and collect baseline information:

1. REDCap Survey Questionnaires:
 1. Compliance questionnaire
 2. Tobacco use history
 3. Demographics
 4. Legal history
 5. Audit C
 6. Butt-out
 7. Environmental Smoke Questionnaire
 8. Social support
 9. Smoking Motivation (WISDM-Brief)
 10. Craving questionnaire
2. Interview

1. Visit screener
2. Medical history and medications
3. NIDA Substance use quick screen
4. Cigarette details
5. Concomitant medications
3. Biomarkers
 1. Smell function will be assessed with the B-SIT Test. Gender-normed standard scores will be used to determine if participants have normal smell function for eligibility.
4. Participants will complete computerized decision-making tasks to gain familiarity prior to the MRI scan. The tasks include a stroop interference task, monetary temporal discounting task, and a Smoking Go/NoGo task. Participants will be shown a powerpoint that explains the screens/images they will see while in the MRI during an odor-cue reactivity task. All tasks will be completed in approximately 15 minutes.
5. At the end of the visit, participants will be asked to keep a log of the cigarettes they smoke each day until their next visit. Participants will receive a daily REDCap survey link via text message using the Twilio service. The survey will ask participants to record the frequency and type of tobacco and alcohol used that day. Participants will be instructed on how to complete the survey and will be provided with a paper log to tally their cigarette use throughout the day. Participants who are unable or unwilling to receive study text messages will track their cigarette use on the paper log only. The REDCap or paper daily cigarette log surveys are not mandatory for participation.

Time commitment: 1.5 hour

Participants will be asked to refrain from smoking for 14 hours prior to MRI Visit 1. A Zoom call (**Remote Visit 1**) and In-person visit (**MRI Visit 1**) will be scheduled.

7.2.2 MRI visit 1

Participants will complete the following procedures in person after refraining from smoking for 14 hours prior to the visit.

Participants will sign their long form written consent at this visit prior to any further study procedures.

1. REDCap Survey Questionnaire
 - a. Nicotine Withdrawal (MNWS)
 - b. Smoking Urges (QSU)
 - c. Craving questionnaire
2. Interview
 - a. Penn State CNMRR MRI Safety
 - b. Scent Ratings post MRI Scan
3. Biomarkers
 - a. Urine collection for cotinine analysis and pregnancy determination: Obtain urine and process pregnancy test for women of child bearing age (have had a period in the past 12 months) who have not had a hysterectomy.
 - b. Saliva collection for potential cotinine analysis, micro RNA (miRNA) biomarker analysis and use in future research.
 - c. Exhaled carbon monoxide will be measured using a hand-held monitor.

4. A member of the study team will first review the MRI safety sheet and determine that it is safe for the participant to be scanned. If safe, participants will complete a one-hour MRI scan that will include the following tasks.

The risks and discomforts associated with this project are the same as that associated with standard clinical MRI and EEG studies, which are minimal. Risk exists from radio frequency heating of the head, but is safe at the specific absorption rate (SAR) limits prescribed by the FDA. The SAR of radiofrequency field exposure is monitored throughout the study and maintained below the limits established by the FDA.

The second risk is the potential danger of the magnetic field, which can produce injury if ferromagnetic devices are accidentally brought into proximity of the magnet. All patients and staff are screened for magnetic objects, and access to the magnet area is restricted. Discomforts may be caused by claustrophobic environment in the MRI scanner to some subjects as well as from the loud tapping noises made during the scan process.

- a. High resolution anatomical scan (~10 minutes)
- b. Monetary temporal discounting task (~15 mins).

Participants will be asked to choose 96 times via button box between two options with specified dollar amounts and time delays to receipt of the money.

[figure not shown]
[figure not shown]

Figure 1. Illustration of monetary temporal discounting task

- c. Tobacco odor cue-reactivity task (~15 minutes)

An odor cue-reactivity task will be used to compare neural reactivity to tobacco, strawberry vanilla, and neutral odors. Two runs of alternating blocks of tobacco smoke odor, strawberry vanilla odor, and neutral odor (propylene glycol) will be delivered for 15 presentations. The odor will be presented for 6 seconds followed by 22 to 38 seconds of no odor (fresh air). A standardized MRI-compatible olfactometer at the Penn State CNMRR will be used to deliver odors inside the scanner at the opening of the participant's nose through plastic Teflon tubing. Participants will wear a respiration belt that will monitor the natural pace of their breathing to deliver the odor prior to inhalation. The odors will be presented in randomized order.

d. Smoking Go/NoGo task (~25 mins)

Using a button box inside the scanner, participants will press a button (Go) as quickly as possible or inhibit their button press (NoGo) when presented with smoking and non-smoking pictures bordered in blue or yellow. Participants will respond to 768 pictures total in pseudorandomized order.

[figure not shown]

Figure 3. Illustration of smoking Go/No Go task.

- Prior to the visit, an unblinded member of the study team will randomize the participant to either the VLNC or NNC cigarette group based on a pre-determined block randomization list. The unblinded study member will identify the cigarette packs with the assigned nicotine content by NRC code and prepare them for redistribution by re-labeling each pack with the participant ID number and a label indicating these are research cigarettes. The unblinded study member will keep records of the RTI log numbers of the packs dispensed to each participant at each visit. At the end of MRI Visit 1 participants will be given an ample 6-week supply of their assigned cigarette (125% of baseline cigarettes per day) and instructed to only smoke study cigarettes until their next scheduled appointment. Participants may contact the study team to receive more study cigarettes if they run out prior to their next visit unless this is more than a 100% increase from their baseline CPD. Participants will be instructed to continue completing the daily REDCap cigarette log surveys that they receive via text message and will also be given paper cigarette logs to track use throughout the day.

Time commitment: 2 hours

7.2.3 Remote visit 1 (scheduled for +1 to +3 day(s) of in person MRI visit)

Participants will complete the following procedures over Zoom

1. REDCap Survey Questionnaire

- a. Depression (CESD)
- b. COPD (CCQ)
- c. Psychological Distress (Kessler K6)
- d. Nicotine Dependence
- e. Anxiety (ASQ)
- f. Sleep Disturbance
- g. Cigarette Liking
- h. Stages of Change
- i. Perceived Stress

2. Interview

- a. Concomitant medications
- b. Adverse event trigger questions

3. Out of scanner tasks

- a. Participants will complete a monetary temporal discounting task. During this computerized task, participants will choose between two options with specified dollar amounts and time delays to receipt of money (see MRI task image below).
- b. Participants will complete a computerized stroop interference task where they will view color words printed in the same color (i.e., blue, red, yellow, green), color words printed in an incongruent color (e.g., “blue” printed in red), and color neutral words printed in color (e.g., “hat” printed in red). Participants will be asked choose what color each word is printed in by pressing a button labeled to indicate each color.

7.2.4 Phone call 1

Participants will be contacted in the 2nd week of the randomization phase to check-in regarding their next scheduled appointment and their success with cigarette tracking and study cigarette compliance.

Time commitment: 15 minutes

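### The Nicotine Dependence questionnaire is first listed 1 to 3 days after the assigned cigarettes are handed out, so a change score on it has no listed pre-exposure starting value

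*Combined protocol and SAP*

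**What the plan says.** Section 7.2.2 sets the start of exposure: "At the end of MRI Visit 1 participants will be given an ample 6-week supply of their assigned cigarette", with the instruction to smoke only those. Randomisation has been done by an unblinded team member before that visit.

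The next contact, in Section 7.2.3, is headed "Remote visit 1 (scheduled for +1 to +3 day(s) of in person MRI visit". Its survey list contains an item called Nicotine Dependence, the only place where that item is named. Sections 7.2.5 (week 3) and 7.2.7 (Remote visit 3, around week 6) repeat it by referring back to Remote visit 1.

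The two contacts before dispensing have their own lists. The final remote screen (Section 7.2.1) includes tobacco use history, WISDM-Brief, a craving questionnaire and an interview item called Cigarette details. MRI Visit 1 (Section 7.2.2) has MNWS, QSU and craving. Neither lists Nicotine Dependence.

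Section 1.2 gives change in smoking dependence as one of two primary endpoints. Section 8.3 (Aim 3) relates BOLD change to reductions in FTND, HONC, MNWS and QSU, cigarettes per day, and quit intention and success. It does not say which visit supplies the baseline for the questionnaire changes.

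**The concern.** A change score measures the effect of an intervention only if its starting value comes before the intervention. Here the first listed score on the dependence questionnaire comes after both randomisation and one to three days on the assigned product. Any arm difference that has arisen by then is subtracted out of the change. If the score were used as a covariate instead, the analysis would adjust for something the intervention may already have altered.

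Aim 3 has a further mismatch. The BOLD change runs from a scan taken before dispensing, while the questionnaire change it is related to starts after dispensing. The two changes therefore do not cover the same period. Section 11.0 expects that reduced-nicotine cigarettes may bring withdrawal symptoms, so the first days cannot simply be taken as neutral.

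**Working it through.** **1. What is listed before and after dispensing** (Sections 7.2.1 to 7.2.8)

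| Measure | Before dispensing | After dispensing |
|---|---|---|
| Nicotine Dependence | none listed | Remote visits 1, 2 and 3 |
| MNWS, QSU | MRI Visit 1 | Remote visit 2, MRI visit 2 |
| Craving | remote screen, MRI Visit 1 | Remote visit 2, MRI visit 2 |
| WISDM-Brief | remote screen | not listed again |
| Cigarettes per day | daily log (not mandatory) | daily log continues |
| BOLD | MRI Visit 1 | MRI visit 2 |

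Nicotine Dependence is the only dependence measure in this table that is repeated later but has no listed value before dispensing. WISDM-Brief has the opposite gap: as listed, it yields no change score.

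**2. Does the window mean after the scan?**
- Remote visit 3 is given a window of -1 to +1 day. The protocol therefore uses a minus sign when it means before, and +1 to +3 means after.
- Remote visit 1 includes adverse event questions, which fits a contact after product has been dispensed.
- Section 14.0 lists payment for MRI visit 1 ahead of Remote visit 1.
- Written consent is given at MRI Visit 1: "Participants will sign their long form written consent at this visit prior to any further study procedures" (Section 7.2.2) and "The subject will sign the consent form during their MRI visit after both screenings have taken place" (Section 5.2.1). Before that, only verbal consent to screening exists, and Section 5.2.2 says of screening: "The screening takes place prior to the randomization portion of the study and involves low risk procedures". Remote visit 1 is not described as screening, so placing it first would put it ahead of written consent.

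**3. Share of exposure before the first listed score.** Take day 0 as dispensing at MRI Visit 1, and the first score on day d = 1 to 3.
- Nominal week 6, day 42: d/42 gives 1/42 = 2.4% to 3/42 = 7.1%.
- Full windows: MRI visit 2 at 42 ± 5 = day 37 to 47; Remote visit 3 within one day of it = day 36 to 48. The limits are 1/48 = 2.1% and 3/36 = 8.3%.

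**4. Period covered by each change.** With MRI visit 2 on day 42, Remote visit 3 falls on day 41 to 43. The questionnaire change spans 41 − 3 = 38 to 43 − 1 = 42 days. The BOLD change spans 42 days and starts at day 0.

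These are shares of exposure time, not of effect. The plan states no figure of its own to reproduce on this point.

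**The case against.** **What stands.** The documents establish that the questionnaire is not listed before dispensing, not that it is not collected. Section 4.4 refers to supporting documents for the screening tools. The content of tobacco use history and of Cigarette details is not given, and either could hold dependence items. Equating Nicotine Dependence with FTND or HONC is an inference. The recall period is not stated either: if the items ask about usual or past smoking, an answer on day 1 to 3 may largely describe smoking before dispensing. One component of an endpoint that Section 1.2 does not define by instrument is affected, by at most a few days.

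**Stronger readings that a reader might infer, and that the documents do not support:**
- *The dependence endpoint has no baseline.* MNWS, QSU, craving and, where kept, the cigarette log do have values before dispensing.
- *The protocol contradicts itself on visit order.* Section 7.2.1 says "A Zoom call (Remote Visit 1) and In-person visit (MRI Visit 1) will be scheduled", naming the remote contact first, but gives no sequence. Section 7.2.5 likewise names MRI visit 2 before Remote visit 3, although the latter may fall a day earlier, so naming order carries no timing. The wording "see MRI task image below" in Section 7.2.3, with the figure in fact above, is an editorial slip.
- *The week-3 change is hit harder.* The share there is larger (1/21 = 4.8% to 3/21 = 14.3%), but Section 8.3 defines no week-3 dependence contrast.
- *A stated fraction of the effect is lost.* The documents give no onset curve. Assuming exponential onset with half-time h, the share of the 6-week effect present at day d is (1 − 2^(−d/h)) / (1 − 2^(−42/h)). This gives 5.5% to 15.8% for h = 14 days and 20.6% to 50.0% for h = 3 days. The answer comes from the assumption, so no such figure can be attributed to the trial.

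**Conclusion.** The point holds in a limited form. As listed, the Nicotine Dependence questionnaire has its first score after randomisation and after 1 to 3 of 42 days on assigned cigarettes (2.4% to 7.1% of exposure; 2.1% to 8.3% across the windows). A change score built on it would not start from a pre-treatment value and would not match the BOLD change in Aim 3. The size and sign of the resulting bias cannot be derived from the documents, and it may be small.

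This rests on three assumptions: that the visit lists are complete, that the questionnaire is the FTND and/or HONC of Section 8.3, and that Remote visit 1 would serve as its baseline, since no earlier administration is listed. It is an inexpensive improvement to the schedule, not a defect that undermines the dependence endpoint as a whole.

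**What to change.** List the dependence scales by name in Section 7.2 at a contact before dispensing, and name that contact as their baseline in Section 8.3. Two places are available:
- **Final remote screen.** It already collects baseline surveys and has no stated abstinence requirement. The drawbacks are a gap of unstated length before the baseline scan, and that the verbal-consent description of screening (Section 5.2.2) must cover the scales.
- **MRI Visit 1, before dispensing.** It follows written consent, falls on the day of the baseline scan and already includes three surveys. The drawback is that answers are given after 14 hours of abstinence. Randomisation has already occurred, but exposure has not.

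If the scales are already collected at screening, one sentence saying so and naming that visit as the baseline is enough.

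For participants already enrolled:
- Label the Remote visit 1 score as post-dispensing and do not use it as a pre-treatment covariate.
- Compare week-6 scores by arm, adjusted for measures taken before dispensing (QSU, MNWS, craving, WISDM-Brief, cigarettes per day).
- Aim 3 needs individual changes, so the week-6 comparison does not replace it. Report the questionnaire-change correlation with its limitation stated.

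The cost is an amendment to the visit schedule and Section 8.3, and a few minutes at an existing contact, with no new visit or instrument. Data already collected cannot be given a pre-dispensing score, and the adjusted week-6 comparison may be less precise than one using the scale's own baseline. The figure reference in Section 7.2.3 can be corrected in the same amendment.
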